### 7.9.2.2 Secondary Objective – UF Change

To demonstrate an improvement from baseline to 6 months in number of UF episodes in subjects with UF at baseline

**Hypothesis:** The change from baseline in UF episodes is not 0.

$$H_0: \mu = 0$$

$$H_A: \mu \neq 0$$

Where  $\mu$  = the change in UF episodes

**Endpoint Definition and Derivation:** A 3-day urinary voiding diary will be used to collect bladder symptoms, including UF episodes. UF episodes include all urinary voids. Calculation of change in UF is defined in the voiding diary analysis section 7.2.2. A negative change in UF episodes represents an improvement.

**Performance Requirements:** The null hypothesis will be rejected if the two-sided p-value is determined to be significant, as described in section 7.5.

**Sample Size Justification:** Data from published studies on TNM outcomes at 6 months were used as a starting point to estimate expected reduction in UF episodes as well as expected patient-to-patient variability. Assumption on the expected mean difference (-2.0 episodes per day) and standard deviations (3.0 episodes per day) were used to assess statistical power. Presuming a two-sided, one-sample t-test with alphas ranging from 0.013 to 0.05, power is calculated to be no less than 98% for any of the scenarios examined with a sample size of 51 subjects (as only 42% of the total 121 subjects in the study are expected to have UF with 10 episodes per day at baseline). Additionally, the minimum detectable difference in mean daily episodes was calculated to be as low as 1.4.

**Rationale for Clinical Relevance:** No published data are available defining minimum clinically meaningful improvement for the change in UF episodes. In the absence of published definitions, assessment of effect size can be used to determine the level of effect. As published by Cohen (1988), an effect size of 0.2 indicates a small effect, 0.5 a modest effect, and 0.8 a large effect. A modest effect size would correspond to a change of -1.5 episodes per day. The assumed mean  $\pm$  standard deviation difference of  $2.0 \pm 3.0$  UF episodes per day (i.e., an effect size = 0.67) for implantable tibial therapy is considered a medium to large effect.

**Analysis Methods:** The analysis for change in UF will be summarized for baseline, at 6 months after implant, and for the change from baseline. If 5% of the data or fewer are missing for the analysis, no imputation will be used, and the objective will be tested using a paired t-test following the multiple testing strategy described in section 7.5. If more than 5% of the data are missing, missing data will be

imputed as specified in section 7.4. If non-normality of the data is detected via a significant ( $p<0.05$ ) Shapiro-Wilk test, a Wilcoxon signed-rank test will replace the t-test.

**Determination of Subjects/Data for Analysis:** The change in UF analysis will include all subjects from the Full Analysis Set (i.e., all implant attempted subjects) who have UF as defined in section 7.1.3.

**Supportive and Sensitivity Analyses:** There are no requirements or expectations for the results of the supporting and sensitivity analyses.

To assess the robustness of the objective results under the influence of missing data, sensitivity analyses will be conducted using alternative missing data methods. The first sensitivity analysis will be completed including subjects from the Secondary Objective (UF Change) Complete Case analysis set. This analysis set will be used for a second sensitivity analysis which will be completed including only subjects who received stimulation ('As treated analysis') at the 6-month follow-up visit. A final complete case sensitivity analysis will be performed comparing the change in UF episodes to a performance goal of 1 episode/day. A Complete Case sensitivity analysis will be provided assessing the UF change from baseline using different definitions of UF (UF defined as  $\geq 8$  and UF defined as  $\geq 12$ ).

UF change from baseline will be assessed over time through 24 months as part of the additional measures.

### 7.9.2.3 Secondary Objective – UPS Change

To demonstrate an improvement from baseline to 6 months in urgency using the Urgency Perception Scale (UPS)

**Hypothesis:** The change from baseline in UPS is not 0.

$$H_0: \mu = 0$$

$$H_A: \mu \neq 0$$

Where  $\mu$  = the change in UPS score

**Endpoint Definition and Derivation:** The UPS will be used to collect OAB urgency. The UPS was developed to assess urgency associated with overactive bladder (OAB). The UPS is a single question assessed at each visit and has 3 options for responses: 1, 'I am usually not able to hold urine'; 2, 'I am usually able to hold urine until I reach the toilet if I go immediately'; and 3, 'I am usually able to finish what I am doing before going to the toilet'. Change from baseline is calculated by subtracting the baseline value from the follow-up value. Therefore, the change can range from -2 to 2 (with positive change indicating an improvement).

**Performance Requirements:** The null hypothesis will be rejected if the two-sided p-value is determined to be significant, as described in section 7.5.

**Sample Size Justification:** Internal data from TNM outcomes were used as a starting point to estimate expected change in UPS as well as patient-to-patient variability in that change. Assumptions on the expected mean difference (0.50) and standard deviation (0.80) were used to assess statistical power. Presuming a two-sided, one-sample t-test with alphas ranging from 0.013 to 0.05, power is calculated to be at least 99% for any of the scenarios examined with a sample size of 121 subjects. Additionally, the minimum detectable change in UPS was calculated to be as low as 0.24 points.

**Rationale for Clinical Relevance:** No published data are available defining minimum clinically meaningful improvement for UPS. In the absence of published definitions, assessment of effect size can be used to determine the level of effect. As published by Cohen (1988), an effect size of 0.2 indicates a small effect, 0.5 a modest effect, and 0.8 a large effect. A modest effect size would correspond to a change of 0.4 in the mean UPS. The assumed mean  $\pm$  standard deviation change of  $0.5 \pm 0.8$  in the UPS (i.e., an effect size = 0.63) for tibial therapy is considered a medium to large effect.

**Analysis Methods:** The analysis for UPS will be summarized for baseline, at 6 months after implant, and for the change from baseline. If 5% of the data or fewer are missing for the analysis, no imputation will be used, and the objective will be tested using a paired t-test following the multiple testing strategy described in section 7.5. If more than 5% of the data are missing, missing data will be imputed as specified in section 7.4. If non-normality of the data is detected via a significant ( $p < 0.05$ ) Shapiro-Wilk test, a Wilcoxon signed-rank test will replace the t-test.

**Determination of Subjects/Data for Analysis:** The UPS analysis will include all subjects from the Full Analysis Set (i.e., all implant attempted subjects) as defined in section 7.1.3 as all subjects are expected to have urgency.

**Supportive and Sensitivity Analyses:** There are no requirements or expectations for the results of the supporting and sensitivity analyses.

To assess the robustness of the objective results under the influence of missing data, sensitivity analyses will be conducted using alternative missing data methods. The first sensitivity analysis will be completed including subjects from the Secondary Objective (UPS) Complete Case analysis set. This analysis set will be used for a second sensitivity analysis which will be completed including only subjects who received stimulation ('As treated analysis') at the 6-month follow-up visit. A third sensitivity analysis will be performed excluding those subjects who report limited problems with urgency, as reported by a baseline score of 3 on the UPS. A final complete case sensitivity analysis will be performed comparing the change in urgency to a performance goal of 0.4.

A supportive analysis will be completed summarizing the percentage of subjects in each category at each visit. The change in UPS will be further categorized as improvement (1-2 point improvement), no change, and worsening (1-2 point worsening), with the number and percentage of subjects summarized for each category.

To test the change in UPS using an alternative statistical analysis method, a supportive analysis will be completed recategorizing the values at each visit as into “not able to hold urine” (response level 1) and “able to hold urine” (levels 2/3). Change from baseline to Month 6 will be tested using Fisher’s exact test for the 2x2 contingency table.

UPS change from baseline will be assessed over time through 24 months as part of the additional measures.

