## **5. Investigation Plan**

This is a prospective, multicenter, single-arm pivotal study to assess safety and effectiveness for the implantable TNM device in subjects with overactive bladder. Subjects who meet all inclusion/exclusion criteria will be implanted with the implantable TNM device. A full list of eligibility criteria can be found in the CIP. Study visits are shown in Figure 1.

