The multiplicity adjustment will be performed for evaluations of the secondary endpoints only. No multiplicity adjustment will be performed for supporting, sensitivity, or subset analyses [REDACTED]

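### The supportive urgency (UPS) analysis tests a within-subject change with Fisher's exact test on an undefined 2x2 table; a paired test is needed

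*SAP*

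**What the plan says.** SAP section 5 describes the design: "This is a prospective, multicenter, single-arm pivotal study". No control group can supply one margin of a 2x2 table.

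In SAP section 7.9.2.3 the UPS is a single item with three levels, and the pairing is explicit: "Change from baseline is calculated by subtracting the baseline value from the follow-up value". The main test is paired: a paired t-test, or Wilcoxon signed-rank if the Shapiro-Wilk test is significant. If more than 5% of data are missing, SAP section 7.4 specifies multiple imputation by ordinal logistic regression followed by a t-test.

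The same section then adds a further analysis, introduced with "To test the change in UPS using an alternative statistical analysis method". The UPS values are split at each visit into level 1 (unable to hold urine) and levels 2/3 (able). The instruction is "Change from baseline to Month 6 will be tested using" Fisher's "exact test for the 2x2 contingency table". The row and column variables are not named.

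On status, the section says "There are no requirements or expectations for the results of the supporting and sensitivity analyses", and SAP section 7.5 says "No multiplicity adjustment will be performed for supporting, sensitivity, or subset analyses". Protocol section 14.5.3 does not contain this test, so it cannot settle the layout. Neither document names a paired test for a binary outcome.

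**The concern.** Fisher's exact test assesses independence of the row and column variables among independent observations. Here each subject contributes two correlated observations, and the question is whether the proportion able differs between the visits. Two layouts fit the SAP wording, and they fail differently.

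- **Baseline status by Month 6 status (one entry per subject).** The null hypothesis is that Month 6 status is unrelated to baseline status. Subjects tend to resemble themselves over time, so this null is usually false whether or not urgency improves.
- **Visit by status (two entries per subject).** The null hypothesis concerns the right two proportions, but 242 paired values are treated as independent. With positive within-subject correlation the test is conservative and loses power.

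The SAP presents this as another way of testing the urgency change, so its p-value could be cited as corroboration. Urgency is one of the three symptoms that SAP section 7.5 requires for the OAB indication. Under the first layout the p-value would say nothing about change. Under the second, a real improvement might not be corroborated. Two programmers could reach opposite conclusions from the same data.

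**Working it through.** **The plan's own figure.** The Fisher analysis has none. For the main UPS test the SAP assumes mean change 0.50, SD 0.80 and n = 121. The noncentrality is 0.50 / (0.80/√121) = 0.50 × 11 / 0.80 = 6.875. Power from the noncentral t exceeds 99.99% at two-sided alpha 0.013 and at 0.05, which agrees with the stated minimum of 99%. The minimum detectable change is 0.238 at alpha 0.05 with 90% power, which agrees with the stated 0.24. The main test is not in question.

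**Inputs for the check.** n = 121 is from the SAP. The documents give neither binary UPS proportions nor a within-subject correlation, so these are assumed and varied.

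**Notation.** Count subjects by baseline then Month 6 status: a = unable-unable, b = unable-able, c = able-unable, d = able-able.

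- Net change depends only on b and c: (b − c)/n is the change in the proportion able.
- Correlation: phi = (ad − bc) / √[(a+b)(c+d)(a+c)(b+d)].
- Baseline-by-Month-6 Fisher uses rows (a, b) and (c, d).
- Visit-by-status Fisher uses rows (a+b, c+d) and (a+c, b+d).
- Exact McNemar is a two-sided binomial test of b out of b + c against 0.5.

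**Three worked tables (n = 121).**

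| a / b / c / d | Unable, baseline → Month 6 | phi | Fisher, baseline by Month 6 | Fisher, visit by status | Exact McNemar |
|---|---|---|---|---|---|
| 50 / 10 / 10 / 51 | 60 → 60 | 0.67 | 4.4e-14 | 1.0 | 1.0 |
| 18 / 52 / 13 / 38 | 70 → 31 | 0.003 | 1.0 | 5.7e-7 | 1.2e-6 |
| 45 / 18 / 6 / 52 | 63 → 51 | 0.62 | 2.6e-12 | 0.16 | 0.023 |

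First row: phi = (50×51 − 10×10)/(60×61) = 2450/3660 = 0.67. There is no change, yet the cross-tabulated Fisher test is overwhelmingly significant.

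Second row: the improvement is large, and the same test gives p = 1.0.

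Third row: McNemar p = 2 × [C(24,0) + … + C(24,6)] / 2^24 = 2 × 190,051 / 16,777,216 = 0.023. The change is (18 − 6)/121 = 9.9 percentage points. Its simple large-sample standard error is √(24 − 12²/121)/121 = 3.9 points, so the 95% CI is about 2.2 to 17.7 points. The visit-by-status test misses this change at p = 0.16.

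**No true change.** Simulated share of trials with p < 0.05, with 40% or 50% able at both visits and 6,000 replicates per setting:

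| Correlation | Fisher, baseline by Month 6 | Fisher, visit by status | Exact McNemar |
|---|---|---|---|
| 0 | 4.0-4.5% | 3.7-3.8% | 3.4-4.2% |
| 0.2 | 55-58% | 1.9-2.1% | 3.6-3.7% |
| 0.4 | 99% | 0.5-0.8% | 2.9-3.3% |
| 0.6 | 100% | 0.03-0.1% | 2.8-3.1% |

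**Power for a rise from 40% to 55% able.**

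| Correlation | Fisher, visit by status | Exact McNemar |
|---|---|---|
| 0 | 59% | 60% |
| 0.2 | 60% | 69% |
| 0.4 | 62% | 81% |
| 0.6 | 63% | 95% |

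Over the same four settings the baseline-by-Month-6 Fisher test rejects in 4%, 57%, 99.6% and 100% of trials. These are almost the rates seen with no change, so the test does not respond to the improvement.

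**The case against.** The strongest reply is that little depends on this analysis. It is supportive, has no required result and lies outside the Hochberg procedure. The same section also reports category percentages by visit, counts of improved, unchanged and worsened subjects, and several sensitivity analyses, so a reader could see the direction and size of change without this p-value. All of that stands, and it limits the severity.

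A second reply is that the dramatic figures belong only to the baseline-by-Month-6 layout. On the visit-by-status layout, type I error stays below 5% at the zero and positive correlations examined, so the only cost there is power. This is right, and the SAP's reference to values at each visit fits that layout at least as well. The text does not settle the choice, however, so the worse reading remains open to whoever programs it.

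A third reply concerns the power loss. The mean UPS change equals the fall in the proportion at level 1 plus the rise in the proportion at level 3. If the planned 0.50 splits evenly, the fall in the proportion unable is 25 points. For falls from 60% to 35% or from 50% to 25%, both tests then have at least 96% power at correlations from 0 to 0.4 and differ by no more than about 2 points; a correlation of 0.6 is impossible with those margins. So near the planned effect the loss is negligible under an even split. The SAP does not give the split, and if most of the change occurs between levels 2 and 3, the binary effect is small and the loss is material.

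Finally, the second worked table needs almost no within-subject correlation, which is unusual for repeated measures. It shows what the test can do and is not a forecast.

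**Conclusion.** The concern holds. As written, the supportive analysis names a test that does not suit paired data and leaves its table undefined. Under the baseline-by-Month-6 layout the p-value is uninformative about change, with rejection in 55% to 100% of trials when nothing has changed and the correlation is 0.2 to 0.6. Under the visit-by-status layout the test is conservative when the correlation is positive. For a 15-point effect (40% to 55% able) it gives up about 9 points of power at correlation 0.2 (69 − 60), 19 at 0.4 (81 − 62) and 32 at 0.6 (95 − 63). The loss is close to nil at zero correlation, or when the binary effect is about 25 points.

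These sizes rest on assumed proportions and correlations. That Fisher's test does not use the pairing correctly under either layout rests on no assumption. The primary result, the Hochberg decision on UPS and the study success criterion are unaffected. This should be corrected before analysis, but it does not threaten the trial's conclusions.

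**What to change.** In SAP section 7.9.2.3, replace the Fisher sentence with one that does three things:

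1. Defines the 2x2 table as baseline status (unable or able) by Month 6 status, one entry per subject, for subjects with UPS at both visits.
2. Tests the change with the exact McNemar test on the discordant pairs.
3. Reports the paired difference in the proportion able to hold urine with its 95% CI, naming the interval method.

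The cost is one SAP sentence and a small change of code. It needs no new data and leaves the sample size, the main UPS test and the multiplicity procedure as they are.

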### 7.9.2.4 Secondary Objective – OAB-q Change

To demonstrate an improvement from baseline to 6 months in quality of life (QoL) using the Overactive Bladder Symptom Quality of Life Questionnaire (OAB-q)

**Hypothesis:** The change from baseline in OAB-q HRQL is not 0.

$$H_0: \mu = 0$$

$$H_A: \mu \neq 0$$

Where  $\mu$  = the change in OAB-q HRQL total score

**Endpoint Definition and Derivation:** The OAB-q will be used to collect quality of life. The OAB-q was developed to assess symptom bother and the impact of overactive bladder (OAB) on health-related quality of life (HRQL). The Health-Related Quality of Life (HRQL) total score is calculated by summing the four subscale scores (coping, concern, sleep, social). For each subscale, if <50% of the items are missing, the subscale is retained with the mean of the items present used to impute the missing items in that subscale. If  $\geq 50\%$  of items in any subscale are missing, the HRQL Total will be missing. A positive change in OAB-q HRQL score represents an improvement.

**Performance Requirements:** The null hypothesis will be rejected if the two-sided p-value is determined to be significant, as described in section 7.5.

**Sample Size Justification:**

Data from a published study on TNM outcomes at 6 months were used as a starting point to estimate expected change in OAB-q HRQL score as well as patient-to-patient variability in that change.

Assumptions on the expected mean change (20 points) and standard deviation (30 points) were used to assess statistical power. Presuming a two-sided, one-sample t-test with alphas ranging from 0.013 to 0.05, power is calculated to be no less than 99% for any of the scenarios examined with a sample size of 121 subjects. Additionally, the minimum detectable change in OAB-q HRQL score was calculated to be as low as 9 points.

**Analysis Methods:** The analysis for OAB-q HRQL total score will be summarized for baseline, at 6 months after implant, and for the change from baseline. If 5% of the data or fewer are missing for the analysis, no imputation will be used, and the objective will be tested using a paired t-test following the multiple

testing strategy described in section 7.5. If more than 5% of the data are missing, missing data will be imputed as specified in section 7.4. If non-normality of the data is detected via a significant ( $p<0.05$ ) Shapiro-Wilk test, a Wilcoxon signed-rank test will replace the t-test.

**Determination of Subjects/Data for Analysis:** The OAB-q total score analysis will include all subjects from the Full Analysis Set (i.e., all implant attempted subjects) as defined in section 7.1.3.

**Supportive and Sensitivity Analyses:** There are no requirements or expectations for the results of the supporting and sensitivity analyses.

To assess the robustness of the objective results under the influence of missing data, sensitivity analyses will be conducted using alternative missing data methods. The first sensitivity analysis will be completed including subjects from the Secondary Objective (OABq HRQL score) Complete Case analysis set. This analysis set will be used for a second sensitivity analysis which will be completed including only subjects who received stimulation ('As treated analysis') at the 6-month follow-up visit. A final complete case sensitivity analysis will be performed comparing the change in OAB-q HRQL to a performance goal of 10.

## 7.10 Safety Evaluation

All AEs and DDs will be collected throughout the study once the informed consent form is signed. AEs and DDs will be coded using the most recent version of Medical Dictionary for Regulatory Affairs (MedDRA). Severity will be assessed by the Investigator. Relatedness and seriousness of the events will be classified by the Investigator, CEC, and the Sponsor. Cases where the Investigator's classification does not match the CEC's classification will be displayed within the final report; however, the CEC's adjudication will be used for data analysis.

Adverse events that occur prior to implant will be summarized. Adverse events that occur on or after tibial neuromodulation implant date through study discontinuation will also be summarized; summaries specific to the timeframe from implant to the 6-month follow-up visit will be included as well as those that include all post-implant follow-up (i.e. though "24 months"). AE tables summarizing adverse device effects (ADE) will also be included. ADE are events deemed related to the neurostimulator, procedure, external device, study aids, or therapy. In addition to tables of overall ADE, summaries by the individual relatedness component will be summarized using the following categories: procedure-related, device-related (neurostimulator/external device), therapy-related, and study aids-related. Resolution (number of events/percentage) of ADE will be summarized using similar time groupings to other summaries. ADE will also be summarized grouping the events by Common Terminology Criteria for Adverse Events (CTCAE) grade.

The denominator for post-implant summaries will be the number of subjects in the All Implanted analysis set, while for pre-implant summaries it will include all enrolled subjects. Events occurring on date of implant will be considered post-implant events.

Summaries of serious adverse events (SAEs) will also be completed in similar ways to AE summaries. Unanticipated Serious Adverse Device Effects (USADE) will be described. Adverse events in subjects with implant attempted but without full implant will also be summarized as part of additional AE summary tables of the Full Analysis Set. Device-related deaths and system modifications will be summarized in detail.

Device deficiencies will be summarized by device type (i.e., communicator, handset, neurostimulator, wireless recharger/charging dock, external patient accessories, and sterile procedure accessories) through the 24 month visit.

Events will be summarized with number of events, number of subjects who experienced the event, and percentage of subjects who experienced one or more events.

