6.1 Duration

The estimated study duration, from first subject enrollment to last subject visit, is expected to last approximately 36 months. The duration of individual subject participation will vary based on timing of study visits; however, participation of an individual subject will be approximately 24 months. Study completion is defined as Sponsor approval of the Final Study Report and closure of all sites.

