10.14.1 Study Exit

A Study Exit eCRF is required for all subjects. Prior to exiting a subject from the study, it is recommended to follow the subject until all ongoing related AEs are resolved or unresolved with no further actions planned. Upon exiting from the study, no further study data will be collected, or study visits will occur for the subject. All data available through the time of the subject's exit will be used for analysis.

Subjects are urged to remain in the study as long as possible but may be exited from the study for any of the following situations:

- Subject lost to follow-up
- Subject death
- Subject did not meet inclusion/exclusion criteria
- Subject was not implanted with an investigational device
- Subject did not provide consent or data use protection authorization
- Subject chose to withdraw (e.g., consent withdrawal, relocation to another geographic location)
- Investigator deemed withdrawal necessary (e.g., medically justified, failure of subject to maintain adequate study compliance)
- Device explant with no planned replacement.

The following information should be collected at study exit:

- Date of exit
- Reason for exit

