14.9 Safety Evaluation

All AEs and DDs will be collected throughout the study once the informed consent form is signed. AEs and DDs will be coded and summarized using the most recent version of Medical Dictionary for Regulatory Affairs (MedDRA). Severity will be assessed by the Investigator. Relatedness and seriousness of the events will be classified by the Investigator, CEC, and the Sponsor. Cases where the Investigator's classification does not match the CEC's classification will be displayed within the final report; however, the CEC's adjudication will be used for data analysis.

Adverse events and DDs that occur prior to implant will be summarized. Adverse events and DDs that occur on or after tibial neuromodulation implant date through study discontinuation will also be summarized; summaries specific to the timeframe from implant to the 6-month follow-up visit will be included. The denominator will be the number of subjects in the All Implanted analysis set. Adverse events in subjects with implant attempted but without full implant will also be summarized. Events that occur in subjects with an unsuccessful implant procedure will be included in the summaries. AEs and DDs will be summarized with number of events, number of subjects who experienced the event, and percentage of subjects who experienced one or more events.

15. Ethics

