## 7.8 Interim Analyses

No interim assessment of effectiveness will be completed. Safety stopping rules are documented in the CIP.

Study progress reports will be submitted annually. Analysis for the purposes of supporting pre-market approval applications will occur once all subjects have completed the 6-month follow-up visit and will include the primary and secondary objectives and detailed safety summaries. Additional measures will be addressed based on available data at time of the pre-market approval application. A final report will be prepared once all data collection has ended and all subjects have completed the 24-month follow-up visit or have been exited. The inferential analysis for the primary and secondary objectives will not be updated for the final report.

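### The all-follow-up harm percentages in SAP 7.10 are not risks at any stated time and, if tabulated at the pre-market cut, would understate 24-month risk

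*SAP*

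**What the plan says.** SAP 7.10 fixes the denominator: "The denominator for post-implant summaries will be the number of subjects in the All Implanted analysis set". Protocol 14.9 agrees: "The denominator will be the number of subjects in the All Implanted analysis set". The statistics are the number of events, the number of subjects with an event, and the "percentage of subjects who experienced one or more events". The readable safety text describes no person-time rate, time-to-event estimate or number at risk.

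SAP 7.10 plans two post-implant windows. One is fixed: "summaries specific to the timeframe from implant to the 6-month follow-up visit will be included". The other is open: "as well as those that include all post-implant follow-up", which the SAP then labels as running through 24 months.

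SAP section 3 says the plan covers both the pre-market and the final report. On timing, SAP 7.8 states: "Analysis for the purposes of supporting pre-market approval applications will occur once all subjects have completed the 6-month follow-up visit". It promises detailed safety summaries for that report without listing the tables. Under Protocol section 6, subjects explanted without replacement leave the study. Under Protocol 10.14.1: "Upon exiting from the study, no further study data will be collected, or study visits will occur for the subject".

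**The concern.** A crude percentage over all implanted subjects estimates a risk only if everyone was observed for the same period. In the fixed 6-month table they nearly are. In the open window they are not. At the pre-market cut, early recruits have been followed for much longer than late ones. In both reports, a subject who withdraws with the device in place stays in the denominator as event-free while still at risk.

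The harms most exposed are those that can occur after the sixth month. Protocol 11.1 lists infection and migration or erosion among the risks after implantation. Protocol 11.3 sets pausing criteria for migration and erosion leading to explant, and judges migration against a previously reported 2.2% for which it gives no time horizon. The device may stay in place after the study, so its late harms weigh in the benefit-risk judgement. A reader who took the open-window label at face value would read a mixture of follow-up times as a 24-month risk.

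**Working it through.** **Inputs**
- Study duration from first enrolment to last visit: "is expected to last approximately 36 months" (Protocol 6.1). Individual participation is about 24 months (same section). Inferred accrual: 36 − 24 = about 12 months.
- The pre-market cut falls when the last subject reaches month 6. With accrual A = 12 months, follow-up then runs from 6 to 6 + 12 = 18 months, taken as uniform.
- Illustrative 24-month risk: 0.058, from the 7/121 in Protocol 11.3. That figure is a pausing threshold and is used here only to set a scale.
- Exit rate after implant: not given. The range 0–30% over 24 months is assumed.

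**The plan's own figure.** 7/121 = 5.79%. The exact (Clopper-Pearson) 90% interval has lower bound 2.75%, which agrees with the 2.7% in Protocol 11.3. The documents give no figure for the bias examined here.

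**Open-window table at the pre-market cut.** Take the event-time distribution F(t) = 1 − exp{−Λ(t/24)^k}, with Λ = −ln(1 − 0.058) = 0.0598. Here k = 1 is a constant hazard, k = 0.5 puts events early and k = 2 puts them late. The expected crude proportion is the mean of F(t) over t from 6 to 6 + A.

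Because the risk is small, F(t) ≈ Λ(t/24)^k, so for A = 12 the ratio to the 24-month risk can be checked by hand:
- k = 1: mean follow-up 12, and 12/24 = 0.50.
- k = 2: (18³ − 6³)/(3 × 12 × 24²) = 5616/20736 = 0.27.
- k = 0.5: (2/3)(18^1.5 − 6^1.5)/(12 × √24) = (2/3)(61.67/58.79) = 0.70.

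Exact results with no exits, as the ratio to the 24-month risk:

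| Accrual | Early (k = 0.5) | Constant (k = 1) | Late (k = 2) |
|---|---|---|---|
| 6 months | 0.62 | 0.38 | 0.15 |
| 12 months | 0.71 | 0.51 | 0.28 |
| 18 months | 0.78 | 0.63 | 0.44 |

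For A = 12, a 24-month risk of 5.8% would appear as 4.1%, 2.9% or 1.6%. Of 121 subjects that is 4.9, 3.6 or 1.9 with an event, against 7.0. With 15% exits over 24 months the constant-hazard ratio falls from 0.51 to 0.49. Setting the 24-month risk at 2% or 10% leaves it at 0.50–0.51.

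**Implant-to-6-month table.** Let exits be exponential with rate μ, where 1 − exp(−24μ) is the 24-month exit fraction. Relative to the true 6-month risk, the crude percentage is 1.00 with no exits, 0.97–0.99 with 15% exits and 0.94–0.97 with 30%.

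**Open-window table in the final report.** Everyone has reached 24 months or exited, so the expected crude proportion is the integral of f(t)exp(−μt) from 0 to 24, where f is the density of F. For k = 1 and 10% exits, 24μ = 0.1054, and the proportion is 0.0598/(0.0598 + 0.1054) × (1 − 0.942 × 0.90) = 0.362 × 0.1522 = 0.0551. The ratio is 0.0551/0.058 = 0.95.

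| Exits over 24 months | Early | Constant | Late |
|---|---|---|---|
| 0% | 1.00 | 1.00 | 1.00 |
| 10% | 0.97 | 0.95 | 0.93 |
| 15% | 0.95 | 0.92 | 0.90 |
| 30% | 0.89 | 0.84 | 0.79 |

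Exits here mean withdrawal and loss to follow-up. Explant does not belong among them. A subject explanted because of migration or erosion is already in the numerator. One explanted for another reason can no longer have either event, and a competing-risk estimate keeps that subject in the denominator as the crude percentage does.

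**The case against.** The best defence is that the plan already has a sound table. The 6-month window is common to all subjects, the pre-market analysis waits for it, and its bias is a few per cent at most under plausible exits. That stands, so it would be wrong to infer that all post-implant harms are reported without regard to follow-up time. The limit is that this table is silent on events after month 6.

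A reader might also infer that the pre-market report will halve the harm rates. The documents do not support that as a flat statement. SAP 7.8 does not say the open-window table goes into that report. The 0.5 needs inferred 12-month accrual, a constant hazard and comparison with a 24-month risk that nobody has been followed long enough to show at that cut. The hazard could also be front-loaded: the post-implant care advice in Protocol 10.1 aims to limit device movement and restricts activity during the first four weeks. Early events move the ratio to 0.71.

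Other safeguards exist: discontinuation by visit and reason (SAP 7.1.1), detailed summaries of system modifications (SAP 7.10), committee trend review (Protocol 13.1) and count-based pausing criteria (Protocol 11.3). Protocol 10.14 also asks for related events to be reported after a subject completes participation, although 10.14.1 ends study data collection at exit. None of these turns the open-window percentage into a risk over a defined period.

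Finally, parts of the additional-measures text in both documents are redacted, so a time-to-event device measure there cannot be excluded. None is described in SAP 7.10.

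**Conclusion.** The point holds for the all-follow-up table only. Its percentage is not a risk at any stated time, and its 24-month label invites that reading. If tabulated at the pre-market cut with accrual of about 12 months, it would show about half of the 24-month risk under a constant hazard, and between 0.28 (late events) and 0.71 (early events) otherwise. Shorter accrual lowers these ratios and longer accrual raises them.

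In the final report the relative shortfall is 3–7% at 10% exits and 11–21% at 30%, or roughly 5–20% overall. It arises only from withdrawal and loss to follow-up. On 7 events in 121 subjects under a constant hazard, that is about 0.4 of a subject (7 × 0.05) at 10% exits and 1.1 (7 × 0.16) at 30%. The accrual pattern, hazard shape and exit rate are assumptions. The 6-month table needs no correction. This should be changed, but it does not affect the efficacy conclusions.

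**What to change.** In SAP 7.10, keep the counts and crude percentages, and add the following for ADEs, SAEs, infection, migration, erosion and explant:

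- Cumulative incidence with 95% confidence interval and number at risk. In the pre-market report give it at 6 months and, as follow-up allows, at 12 months. Under uniform accrual, (18 − 12)/(18 − 6) = half of the subjects, about 60 of 121 before exits, would have reached 12 months. In the final report give it at 6, 12 and 24 months.
- Censoring at exit or last contact. Treat death, and explant for another reason where it removes the risk of the event, as competing events. State that the estimate assumes that withdrawal is unrelated to the harm.
- Events per 100 subject-years, and the distribution of follow-up at each data cut.
- A sentence saying that the crude all-follow-up percentage is not a 24-month rate, and whether that table appears in the pre-market report.

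The cost is SAP wording and a few standard tables. Explant and exit dates and adverse event reports are already collected, and no clinical procedure changes. Reported late-harm rates will be somewhat higher than the crude percentages.
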